### **6.3.3 Anticipated risks and safety concerns of the study drug**

It is anticipated that the patients entering the roll-over protocol have tolerated everolimus treatment and are anticipated to benefit from continued treatment.

Guidelines and recommendations for the management of specific everolimus study drug induced toxicities (hyperglycemia, hyperlipidemia, stomatitis, infectious pneumonitis, reactivation of Hepatitis B and C) are provided in the current everolimus Investigator Brochure.

## **6.4 Concomitant medications**

### **6.4.1 Permitted concomitant therapy**

In general, concomitant medications/therapies deemed necessary for the supportive care of the patient is permitted.

### **6.4.2 Permitted concomitant therapy requiring caution and/or action**

Everolimus is metabolized by CYP3A4 in the liver and to some extent in the intestinal wall. Therefore, the following are recommended:

- Co-administration with strong inhibitors of CYP3A4 (e.g., ketoconazole, itraconazole, ritonavir) or P-glycoprotein (PgP) inhibitor should be avoided.
- Co-administration with moderate CYP3A4 inhibitors (e.g., erythromycin, fluconazole) or PgP inhibitors should be used with caution. If a patient requires co-administration of moderate CYP3A4 inhibitors or PgP inhibitors, reduce the dose of study drug to half the currently used dose. Additional dose reductions to every other day may be required to manage toxicities. If the inhibitor is discontinued, the study drug dose should be returned to the dose used prior to initiation of the moderate CYP3A4/PgP inhibitor.
- Seville orange, star fruit, grapefruit and their juices affect P450 and PgP activity. Concomitant use should be avoided.
- Co-administration with strong inducers of CYP3A4 should be avoided. If a patient requires co-administration of strong CYP3A4 inducers (i.e., phenytoin, carbamazepine, rifampin, rifabutin, phenobarbital, St. John’s wort), an increase in the dose of study drug up to twice the currently used daily dose should be considered, 5mg increments. Enzyme induction usually occurs within 7-10 days; therefore study drug dose should be increased by one increment 7 days after the start of the inducer therapy. If no safety concerns are seen within the next 7 days, the dose can be increased again one additional increment up

to a maximum of twice the daily dose used prior to initiation of the strong CYP3A4 inducer.

- This dose adjustment of study drug is intended to achieve similar AUC to the range observed without inducers. However, there are no clinical data with this dose adjustment in patients receiving strong CYP3A4 inducers. If the strong inducer is discontinued the study drug dose should be returned to the dose used prior to initiation of the strong CYP3A4/PgP inducer.

Please refer to [Table 6-3](#) listing relevant inducers and inhibitors of CYP3A and to [Table 6-4](#) for a list of relevant substrates, inducers, and inhibitors of PgP. Please refer to the most recent Investigator's Brochure for a complete list.

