**Table 6-4 Clinically relevant drug interactions: substrates, inducers, inhibitors of Pgp and Pgp/CYP3A dual inhibitors**

Substrates
colchicine, digoxin, fexofenadine, indinavir, paclitaxel, talinolol, topotecan, vincristine, everolimus
Inducers
rifampin, St John's wort
Pgp Inhibitors and Pgp/CYP3A Dual Inhibitors
amiodarone, azithromycin, captopril, carvedilol, clarithromycin, conivaptan, diltiazem, dronedarone, elacridar, erythromycin, felodipine, fexofenadine, fluvoxamine, ginkgo (ginkgo biloba), indinavir, itraconazole, lopinavir, mibefradil, milk thistle (silybum marianum), nelfinavir, nifedipine, nitrendipine, paroxetine, quercetin, quinidine, ranolazine, rifampin, ritonavir, saquinavir, Schisandra chinensis, St John's wort (hypericum perforatum), talinolol, Telaprevir, telmisartan, ticagrelor, tipranavir, tolvaptan, valsopodar, verapamil
Reference: Internal Clinical Pharmacology Drug-drug interaction (DDI) memo, updated 29-Oct-2012 which summarizes DDI data from three sources including the FDA's "Guidance for Industry, Drug Interaction Studies", the University of Washington's Drug Interaction Database, and Indiana University School of Medicine's Drug Interaction Table.

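### Protocol 6.4.2 gives PgP inhibitors two different instructions, and its dose-adjustment rules do not fit the stated doses and tablets, most clearly at 2.5 mg/day

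*Protocol*

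**What the plan says.** Protocol 6.4.2 handles interacting drugs in successive bullets.

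- **Bullet 1:** "Co-administration with strong inhibitors of CYP3A4 (e.g., ketoconazole, itraconazole, ritonavir) or P-glycoprotein (PgP) inhibitor should be avoided".
- **Bullet 2:** moderate CYP3A4 inhibitors or PgP inhibitors call for caution. It continues: "If a patient requires co-administration of moderate CYP3A4 inhibitors or PgP inhibitors, reduce the dose of study drug to half the currently used dose". It then allows a further step: "Additional dose reductions to every other day may be required to manage toxicities".
- **Strong-inducer bullet:** "Co-administration with strong inducers of CYP3A4 should be avoided. If a patient requires co-administration of strong CYP3A4 inducers" (agents listed), "an increase in the dose of study drug up to twice the currently used daily dose should be considered, 5mg increments". On timing it says "therefore study drug dose should be increased by one increment 7 days after the start of the inducer therapy". A second increment may follow, "to a maximum of twice the daily dose used prior to initiation of the strong CYP3A4 inducer".

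Table 6-3 grades CYP3A inhibitors (strong, moderate) and inducers (strong, moderate, weak). Table 6-4 puts PgP inhibitors and PgP/CYP3A dual inhibitors in one ungraded list, which begins "amiodarone, azithromycin, captopril, carvedilol, clarithromycin, conivaptan".

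The dose range of 2.5-10 mg/day appears in the protocol summary, Table 6-1 and 6.1.4. Section 6.1.1 names tablet strengths of 2.5, 5 and 10 mg and requires once-daily dosing with tablets swallowed whole.

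**The concern.** There are two problems.

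1. A PgP inhibitor falls under both bullet 1 (avoid) and bullet 2 (caution, and halve the everolimus dose if it is needed). Two sites faced with the same drug could act differently, and each could point to the text.
2. The halving rule, the 5 mg increment and the two-fold cap do not all work over the stated dose range with the named tablets.

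What is at stake is clear instruction on exposure. The Pharmacokinetics text in the protocol background reports that strong CYP3A4 inhibitors raised everolimus blood levels, and that drugs acting on PgP may change its absorption and elimination. Section 6.4.2 itself says the inducer adjustment has no clinical data behind it. SAP 2.4.2 states that concomitant medication is not collected, so differing site practice may be hard to see afterwards.

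**Working it through.** **Part 1: which bullet applies to a PgP inhibitor?**

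Bullet 1 attaches the word strong to CYP3A4 inhibitors and gives PgP inhibitors no grade. Bullet 2 attaches moderate to CYP3A4 inhibitors and again gives PgP inhibitors no grade. The only help left is to look up each Table 6-4 agent in Table 6-3.

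| Table 6-4 PgP or dual inhibitors | Count |
|---|---|
| Full list | 39 |
| Strong CYP3A inhibitor in Table 6-3 (e.g. clarithromycin, itraconazole, ritonavir) | 11 |
| Moderate CYP3A inhibitor (diltiazem, dronedarone, erythromycin, verapamil) | 4 |
| Strong CYP3A inducer (rifampin, St John's wort) | 2 |
| None of these: 39 − 11 − 4 − 2 | 22 |

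The 22 include amiodarone, azithromycin, captopril and carvedilol. One of them, ginkgo, is in Table 6-3 as a weak inducer, which does not settle the question.

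**Part 2: do the dose rules fit the doses?**

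Inputs: tablets of 2.5, 5 and 10 mg, taken whole (6.1.1); range 2.5-10 mg/day (Table 6-1, 6.1.4); halving, 5 mg increment and two-fold cap (6.4.2).

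Assumption: the doses checked are those that whole tablets can make within the range, namely 2.5, 5, 7.5 and 10 mg/day. The documents give a range, not a list of doses, and 7.5 mg/day (5 + 2.5) is not named.

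For a daily dose d: half = d/2; first step = d + 5; second step = d + 10; cap = 2d. A dose can be made if it is a multiple of 2.5 mg.

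| d (mg/day) | Half | Can be made? | First step | Cap | First step within cap? | First step ≤ 10 mg/day? | Second step |
|---|---|---|---|---|---|---|---|
| 2.5 | 1.25 | No; also below range | 7.5 | 5 | No | Yes | 12.5, above cap |
| 5 | 2.5 | Yes | 10 | 10 | Yes | Yes | 15, above cap |
| 7.5 | 3.75 | No | 12.5 | 15 | Yes | No | 17.5, above cap |
| 10 | 5 | Yes | 15 | 20 | Yes | No | 20, equal to cap but above 10 mg/day |

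At 2.5 mg/day the first increment is 7.5/2.5 = 3 times the prior dose, against a limit of 2 times. If the cap prevails, no 5 mg step is possible. Taking 2.5 mg every other day would average 1.25 mg/day, but 6.4.2 offers that schedule only as a further reduction for toxicity.

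**Minor point.** Table 6-4 lists rifampin and St John's wort both as PgP inducers and among the PgP or dual inhibitors. The strong-inducer bullet names both and most likely governs. The Pharmacokinetics text agrees for rifampin. This needs only a note to the table.

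**The case against.** **The two bullets can be read together.** Section 6.4.2 covers permitted therapies and words its advice as recommendations, and the prohibited therapies in 6.4.3 are systemic anticancer agents only. Bullet 1 could therefore mean avoid by default, with bullet 2 covering patients who need the drug. That is a reasonable reading, but it has to be inferred. The strong-inducer bullet states that sequence outright; for PgP inhibitors the conditional sentence follows the caution wording in a separate bullet.

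**The count of 22 depends on how the bullets are read.** It assumes that the CYP3A grade decides for dual agents, which the protocol does not say. Read literally, bullet 1 also covers erythromycin, which is bullet 2's own example, so the overlap is wider. Under avoid-unless-required, few or no agents conflict. The count shows how many agents Table 6-3 leaves open; it is not a count of affected patients.

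**Guidance is delegated.** Section 6.1.1 refers to the Investigator's Brochure and 6.3 for dosing guidance on PgP and CYP3A4 interactions, and 6.3.1 leaves dose changes to the investigator with the Brochure. The Brochure was not available for this review and may resolve the matter in practice. It does not remove two differing sentences from the protocol.

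**Part 2 mixes contradiction with silence.** This is fair. The 7.5 mg/day row rests on an assumption. Going above 10 mg/day under an interaction rule that has its own cap may be intended; the text is silent, although the range also stands in Table 6-1 and the summary. Sections 6.1.1 and 6.6.1 allow local commercial material or locally approved forms, but no other strength is named. The 2.5 mg/day increment-and-cap conflict needs none of these qualifications, because it lies within one bullet.

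**Reach is not shown.** SAP 2.1 reports 34 patients, and neither document gives their doses. This stands.

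**Conclusion.** The concern holds. As written, 6.4.2 gives ungraded PgP inhibitors two instructions, and 22 of the 39 agents in Table 6-4 have no Table 6-3 entry that settles which one applies.

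At 2.5 mg/day, which is both the lower end of the range and a supplied strength, the 5 mg step breaks the rule's own cap and the halved dose cannot be given with the named whole tablets. At 5 mg/day halving and one step both fit. At 10 mg/day halving fits, but the inducer steps leave the stated range. At 7.5 mg/day, if that dose is used, the halved dose cannot be made and the first step leaves the range.

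This should be corrected as a matter of patient-safety clarity. The wording and the arithmetic are certain; how many patients it touches is unknown. It affects no sample size, hypothesis test or planned analysis.

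**What to change.** The sponsor should reconcile Protocol 6.1.1, 6.1.4, 6.4.2, Table 6-3 and Table 6-4 so that:

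- PgP inhibitors have one instruction;
- the halving rule, increment, cap, dose range and tablet strengths agree with each other at every dose in use;
- the text says whether 2.5-10 mg/day limits interaction adjustments;
- a note says which 6.4.2 instruction applies to rifampin and St John's wort.

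The content of those rules is for the sponsor's clinical team; none is proposed here.

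The cost is a written amendment under Protocol 12.1, with sponsor and IRB/IEC/REB approval and health authority approval where required. No new data collection is needed.

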**Table 6-3 Clinically relevant drug interactions: inducers, and inhibitors of isoenzyme CYP3A**

---

**Inducers**

**Strong inducers:**

avasimibe, carbamazepine, mitotane, phenobarbital, phenytoin, rifabutin, rifampin (rifampicin), St. John's wort (hypericum perforatum)

**Moderate inducers:**

bosentan, efavirenz, etravirine, genistein, modafinil, nafcillin, ritonavir, [talviraline], thioridazine, tipranavir

**Weak inducers:**

amprenavir, aprepitant, armodafinil (R-modafinil), bexarotene, clobazam, danshen, dexamethasone, Echinacea, garlic (allium sativum), ginkgo (ginkgo biloba), glycyrrhizin, methylprednisolone, nevirapine, oxcarbazepine, pioglitazone, prednisone, [pleconaril], primidone, raltegravir, rufinamide, sorafenib, telaprevir, terbinafine, topiramate, [troglitazone], vinblastine

---

**Inhibitors**

**Strong inhibitors:**

**boceprevir**, clarithromycin, cobicistat, conivaptan, elvitegravir, indinavir, itraconazole, ketoconazole, lopinavir, mibefradil, nefazodone, nelfinavir, posaconazole ([Krishna et al 2009](#)), ritonavir, saquinavir, **telaprevir**, telithromycin, tipranavir, troleandomycin, voriconazole

**Moderate inhibitors:**

Amprenavir, aprepitant, atazanavir, casopitant, cimetidine, ciprofloxacin, cyclosporine, darunavir, diltiazem, dronedarone, erythromycin, fluconazole, fosamprenavir, grapefruit juice (citrus parasidi fruit juice), imatinib, schisandra sphenanthera, tofisopam, verapamil

---

**Table 6-4 Clinically relevant drug interactions: substrates, inducers, inhibitors of Pgp and Pgp/CYP3A dual inhibitors**

Substrates
colchicine, digoxin, fexofenadine, indinavir, paclitaxel, talinolol, topotecan, vincristine, everolimus
Inducers
rifampin, St John's wort
Pgp Inhibitors and Pgp/CYP3A Dual Inhibitors
amiodarone, azithromycin, captopril, carvedilol, clarithromycin, conivaptan, diltiazem, dronedarone, elacridar, erythromycin, felodipine, fexofenadine, fluvoxamine, ginkgo (ginkgo biloba), indinavir, itraconazole, lopinavir, mibefradil, milk thistle (silybum marianum), nelfinavir, nifedipine, nitrendipine, paroxetine, quercetin, quinidine, ranolazine, rifampin, ritonavir, saquinavir, Schisandra chinensis, St John's wort (hypericum perforatum), talinolol, Telaprevir, telmisartan, ticagrelor, tipranavir, tolvaptan, valsopodar, verapamil
Reference: Internal Clinical Pharmacology Drug-drug interaction (DDI) memo, updated 29-Oct-2012 which summarizes DDI data from three sources including the FDA's "Guidance for Industry, Drug Interaction Studies", the University of Washington's Drug Interaction Database, and Indiana University School of Medicine's Drug Interaction Table.

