## Pharmacokinetics

Everolimus is rapidly absorbed after oral administration, with a median time to peak blood levels ( $t_{max}$ ) of 1-2 hours postdose. The extent of absorption is estimated at above 11%. The area under the blood concentration-time curve (AUC) is dose-proportional over the dose range of 5 to 70 mg tested while maximum blood concentration  $C_{max}$  appears to plateau at dose levels higher than 20 mg. The terminal half-life in cancer patients averaged 30 hours, which is similar to that in healthy subjects. A high-fat meal altered the absorption of everolimus with 1.3 hour delay in  $t_{max}$ , a 60% reduction in  $C_{max}$  and a 16% reduction in AUC. In whole blood, approximately 80% of everolimus is contained in red blood cells. Of the fraction of drug contained in plasma, 74% is protein-bound. The apparent distribution volume ( $V_z/F$ ) after a single dose was 4.7 L/kg. Everolimus is eliminated by metabolism, mainly by hydroxylation, then excreted into the feces >80%.

Everolimus is mainly metabolized by CYP3A4 in the liver and to some extent in the intestinal wall. Everolimus is also a substrate of P-glycoprotein (PgP). Therefore, absorption and subsequent elimination of systemically absorbed everolimus may be influenced by medicinal products that interact with CYP3A4 and/or P-glycoprotein. In vitro studies showed that everolimus is a competitive inhibitor of CYP3A4 and of CYP2D6 substrates, potentially increasing the concentrations of medicinal products eliminated by these enzymes. In two phase III clinical trials in patients following kidney transplantation, strong inhibitors of CYP3A4 (azoles, antifungals, cyclosporine, erythromycin) have been shown to reduce the clearance of everolimus therapy thereby increasing everolimus blood levels. Similarly, Rifampin, a strong inducer of CYP3A4, increases the clearance of everolimus thereby reducing everolimus blood levels. Another drug-drug interaction study of everolimus administered with a sensitive CYP3A4 substrate midazolam showed that while everolimus did not influence the hepatic metabolism of midazolam, it led to minor increases in bioavailability of midazolam likely due to influences of pre-systemic metabolism. Caution should be exercised when co-administering everolimus with CYP3A4 inhibitors, inducers, or substrates with a narrow therapeutic index.

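### Protocol 6.4.2 with Tables 6-3 and 6-4 places rifampin and St John's wort under two opposed dose rules and does not say which prevails

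*Protocol*

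**What the plan says.** Three places in the protocol bear on the point.

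- **Section 6.4.2, inhibitor bullets.** The first says that PgP inhibitors, like strong CYP3A4 inhibitors, should be avoided. The second allows moderate CYP3A4 inhibitors or PgP inhibitors with caution and adds: "If a patient requires co-administration of moderate CYP3A4 inhibitors or PgP inhibitors, reduce the dose of study drug to half the currently used dose". Neither bullet names rifampin or St John's wort.
- **Section 6.4.2, inducer bullet.** Strong CYP3A4 inducers should be avoided. If one is required, "an increase in the dose of study drug up to twice the currently used daily dose should be considered", in 5 mg increments. The first step comes 7 days after the inducer starts, and a further step is allowed only if the next 7 days raise no safety concern. The bullet names its drugs: "phenytoin, carbamazepine, rifampin, rifabutin, phenobarbital, St. John’s wort".
- **Tables 6-3 and 6-4.** Section 6.4.2 refers sites to both. Table 6-3 lists both drugs as strong CYP3A inducers. Table 6-4 gives its PgP inducers as "rifampin, St John's wort" and then repeats both drugs in its row of PgP inhibitors and dual PgP/CYP3A inhibitors: "ranolazine, rifampin, ritonavir, saquinavir, Schisandra chinensis", followed directly by St John's wort.

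The pharmacokinetics text in section 1.2.1.2 describes rifampin in one direction only: "Rifampin, a strong inducer of CYP3A4, increases the clearance of everolimus thereby reducing everolimus blood levels".

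**The concern.** Section 6.4.2 attaches its dose rules to classes of drug and relies on the tables to say which drugs belong to which class. A drug may belong to more than one class, and that alone is no error. The difficulty is that the two classes here carry opposite dose rules, and neither 6.4.2 nor the tables say which rule applies to a drug found in both. Two sites could each follow the text and move everolimus in opposite directions for the same co-medication. One direction lowers the dose in a patient kept on study because of benefit; the other raises it in a study whose primary objective is safety.

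There is a smaller analytical side. SAP section 2.8.1 summarises dose adjustments, cumulative dose and dose intensity, while SAP section 2.4.2 says that concomitant medication is not collected. A dose change made for this reason would enter those summaries, but could not be traced systematically to its cause.

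**Working it through.** The plan states no figure to reproduce. The check has two parts: which drugs fall under both rules, and how far apart the rules are.

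**1. Which drugs are affected.** Three inducer lists were compared with the Table 6-4 inhibitor row.

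| Inducer list | Drugs also in the Table 6-4 inhibitor row |
|---|---|
| Drugs named in the 6.4.2 inducer bullet | rifampin, St John's wort |
| Table 6-3 strong inducers ("phenobarbital, phenytoin, rifabutin, rifampin (rifampicin), St. John's wort (hypericum perforatum" is part of this row) | rifampin, St John's wort |
| Table 6-4 PgP inducers | rifampin, St John's wort |

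Each comparison gives the same two drugs. Ritonavir, tipranavir, telaprevir and ginkgo also appear both as inducers in Table 6-3 and as inhibitors in Table 6-4. Table 6-3 grades them as moderate or weak inducers, and 6.4.2 has no dose-raising rule for those grades, so they meet no opposed rule. The grade of strong for the two affected drugs comes from 6.4.2 and Table 6-3; Table 6-4 does not grade its inducers.

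**2. How far apart the rules are.** Let d be the current daily dose.

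- PgP-inhibitor rule: d × 0.5, with no waiting time stated.
- Strong-inducer rule: anywhere from d (the increase is considered and not made) to at most 2 × d.

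| Current dose (mg/day) | Inhibitor rule | Ceiling of inducer rule | Within the stated 2.5 to 10 mg/day? |
|---|---|---|---|
| 2.5 | 2.5 × 0.5 = 1.25 | 2.5 × 2 = 5 | 1.25 is below the range |
| 5 | 5 × 0.5 = 2.5 | 5 × 2 = 10 | both inside |
| 10 | 10 × 0.5 = 5 | 10 × 2 = 20 | 20 is above the range |

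The range is the one in Table 6-1 and section 6.1.4. The cleanest case is 5 mg/day, because both results stay inside it. At 10 mg/day the ceiling needs two 5 mg steps (10 to 15 to 20), so it is reached no earlier than 7 + 7 = 14 days after the inducer starts.

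The ratio of ceiling to halved dose is 2d / 0.5d = 4 at every dose. If the increase is considered and declined, the ratio is d / 0.5d = 2. The literal gap therefore runs from two-fold to four-fold, and four-fold is its upper limit.

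**3. Is there a precedence rule?** None appears in 6.4.2 or in either table. Section 6.4.2 cites the Investigator's Brochure for a complete list of drugs, not for deciding between two listings.

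**The case against.** The strongest reply is that the two rules do not stand on an equal footing. The inducer bullet names both drugs in its own text. The halving rule reaches them only through a class term and a merged table heading. The pharmacokinetics section describes rifampin only as lowering everolimus levels. A careful reader could infer that the inducer bullet is meant to govern. That is a fair inference, but the protocol does not state it, and the difference in wording pulls the other way: the increase is something to consider, whereas the halving is worded as a direct step.

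Second, both classes are to be avoided, so the first message is the same under either listing. This stands, and it confines the conflict to patients who require the drug. That is also the only situation in which either dose rule operates, so it does not resolve the conflict.

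Third, the bullets are introduced as recommendations, and section 6.3.1 leaves dose changes to the investigator in conjunction with the Investigator's Brochure. Neither the brochure nor the internal memo cited under Table 6-4 is available here, and either may explain the dual listing. This lowers the weight of the point, but discretion does not reconcile two opposed written recommendations.

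A reader might go further and infer that the protocol orders a doubling and a halving together, or that patients face a four-fold dose error. The text does not support that. The increase is optional, stepwise and capped, and four-fold compares a halving with that cap.

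**Conclusion.** The inconsistency is real and lies on the face of the text, but it is narrow. It concerns two drugs, and only patients who require one of them. For such a patient the literal readings at 5 mg/day are 2.5 mg against at most 10 mg. At 10 mg/day the ceiling of 20 mg would also conflict with the protocol's stated dose range.

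The size rests on reading both rules literally and on nothing in the Investigator's Brochure settling the matter. The documents do not say how many patients took either drug. SAP section 2.1 reports 34 patients enrolled, 11 of whom had already discontinued when the amendment was released.

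A reader might also infer that the primary safety results are compromised. The documents do not show this: no exposed patient is described, the analysis is descriptive with no hypothesis tested, and no effect on the frequency or severity of AEs/SAEs is demonstrated. This is an internal inconsistency in dosing guidance, not a choice of design. It should be corrected, but it falls short of a must-fix. Nothing here takes a view on which instruction is right.

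**What to change.** The sponsor should reconcile section 6.4.2, Table 6-3 and Table 6-4 so that rifampin and St John's wort each lead to a single dose instruction. Either of two edits would do: correct the listing in the tables, or add a footnote saying which 6.4.2 bullet governs a drug listed as both inducer and inhibitor. Which instruction applies is for the sponsor's clinical pharmacology group to decide. In the same edit the sponsor should reconcile the 6.4.2 rules with the 2.5 to 10 mg/day range, because they can lead outside it at either end.

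The cost is a table correction or footnote in a protocol amendment and a notification to sites. No new visits, data collection or analyses are needed.
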